10.6.3 Rhythm throughout 3 Years Follow-up

For this secondary endpoint, the following definition will be used:

- % subjects in sinus rhythm at a specific visit: This variable will refer to the data captured at the visit. Details will be defined when preparing analysis programs.
- % subjects with recurrent AF/AT at a specific visit: This variable will also refer to the time period after previous visit up to the visit analyzed (including data captured at the visit analyzed). A subject has recurrent AF/AT if AF or AT is documented at any TTM, Holter or ECG within this timeframe (additional observations of any other rhythms at the same TTM; Holter or ECG are allowed).

To analyze this secondary effectiveness endpoint, rhythm (% subjects in sinus rhythm, % subjects with recurrent AF/AT) throughout 3 years follow-up, the number of subjects and percentage of subjects in sinus rhythm and the number and percentage of subjects with recurrent AF/AT at each visit during the 3 year follow-up time will be summarized and listed by treatment group at each follow-up visit. The analyses will be performed in both ITT and PP populations. Cross-over subjects will be completely excluded in the PP population.

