### **11.2 Schedule of Examinations**

#### **11.2.1 Study Visits and Phone Follow-up**

Table 1 displays the required schedule for subject treatments and evaluations for Test and Control Groups. Sites participating in this study have been selected upon their capabilities to successfully carry out those assessments. Subjects will need to return to the hospital for a follow-up clinical visit at 3 months, 6 months, 1 year, 2 years and 3 years. Follow-up by phone will be conducted for all subjects at 9 months, 18 months and 30 months. Arrhythmia monitoring assessments, as described in Table 1, will be discontinued once subjects have progressed to persistent AF/AT.

All subjects will be followed through 3-years. Subjects who reach the primary endpoint (progress to persistent AF/AT) will only have to return for the final visit at 3 years; however, they will be followed for safety through the 3-years study period by their hospital and all adverse events are to be reported by the investigator as per protocol requirements. Subjects in the Test Group who undergo a repeat ablation procedure will continue follow-up according to the schedule of their index (first) ablation procedure. Thus, subject visits will be counted from the time of the index ablation procedure and not from the date of the repeat ablation procedure. Subjects in the Control Group who undergo an ablation procedure (cross-over), will continue follow-up according to their initial schedule.

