### **Transtelephonic monitoring (TTM)**

All subjects (test and control) will be provided with a TTM device to enable transmission of scheduled and symptom-triggered ECG recordings per the schedule described in Table 1. Both symptomatic and asymptomatic recordings will be analyzed by a Core Lab. Subjects will be trained by the study site personnel on the use of the TTM device and transmission of the recordings. A study specific Core Lab instruction manual, including procedures to be followed, will be made available.

TTM monitoring (both groups) will be conducted as follows:

- Start TTM monitoring at Day 104
- Daily TTM monitoring if symptoms present (to capture symptomatic episodes).
- Weekly TTM monitoring as from Day 104 until Day 300 (to capture some asymptomatic episodes)
- Monthly TTM monitoring as from Day 300 until last study visit (3 Year) (to capture some asymptomatic episodes).

→ If AF is present, the subject will be contacted to begin daily monitoring for 7 consecutive days.

→ Discontinue TTM monitoring when AF is present for 7 consecutive days or requires termination by cardioversion after 48 hours (primary endpoint reached).

Copies of TTM reports are to be filed in the subject's medical chart.

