8. GENERAL ISSUES FOR STATISTICAL ANALYSIS

8.1 General Statistical Methodology

Descriptive summaries will be provided where appropriate for each of the primary and secondary variables. Tables in the ITT population will summarize data by randomized treatment, tables in the PP and Safety populations will summarize data by treatment actually received if not otherwise specified.

Primary and secondary effectiveness analysis will be conducted in the ITT and the PP populations. All safety data analyses will be performed in the Safety Population.

Health economic and QoL tables will be completed for the ITT population unless otherwise specified. According to the protocol it was planned to use the PP population for health economic and QoL tables, but this was changed to ITT population to perform the analysis based on the randomized treatment groups.

Continuous, quantitative, variable summaries will include the number of subjects (N) with non-missing values, mean, standard deviation (SD), median, minimum, maximum, and quartiles, unless otherwise specified.

Categorical, qualitative, variable summaries will include the frequency and percentage (where applicable) of subjects who are in the particular category. In general, the denominator for the percentage calculation will be based upon the total number of subjects in the study population for the treatment groups unless otherwise specified.

The baseline value will be defined as value entered to the screening/baseline page of the eCRF (terminology screening/baseline is not used consistently in eCRF, but there is only one screening/baseline assessment planned according to protocol).

All analyses will be performed using SAS[®] Software version 9.1.3 or later. ADDPLAN[®] version 5.0.2 or later and East version 5.3 or later may also be used.

For re-calculating of operating characteristics for the analyses of the primary endpoint, the software WinLD will be used.

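### After progression, subjects normally have no new recording but stay in the denominator, so SAP 10.6.3 shows most of them as free of recurrent AF/AT at later interim visits

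*SAP*

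**What the plan says.** SAP 10.6.3 defines recurrence at a visit from recordings: "A subject has recurrent AF/AT if AF or AT is documented at any TTM, Holter or ECG within this timeframe". On the timeframe it says "This variable will also refer to the time period after previous visit up to the visit analyzed". Each visit therefore needs fresh documentation, and earlier progression is not carried forward. The section sets no denominator and has no rule for subjects who have already progressed. For the companion measure, the percentage in sinus rhythm, it adds only "Details will be defined when preparing analysis programs".

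SAP 8.1 gives a general default, which other sections may override: "the denominator for the percentage calculation will be based upon the total number of subjects in the study population for the treatment groups". The ITT population in SAP 7 contains every randomized subject, so progressed subjects remain in it.

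Protocol 11.2.1 states: "Arrhythmia monitoring assessments, as described in Table 1, will be discontinued once subjects have progressed to persistent AF/AT". On visits it states: "Subjects who reach the primary endpoint (progress to persistent AF/AT) will only have to return for the final visit at 3 years". Protocol 11.4.1 and 11.4.2 repeat this for the two arms. In Table 1 of the protocol, the ECG is collected only where it was done as standard of care, and this includes the Year 3 visit.

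**The concern.** The numerator depends on recordings that the protocol stops making once a subject reaches the primary endpoint. Someone who progresses counts as recurrent in the window of progression and then, with no new tracing, counts as not recurrent at the following interim visits. The Kaplan-Meier analysis would show that person as progressed while the rhythm table for the same visit shows no recurrent AF/AT.

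The effect builds up over follow-up and is larger in the arm that progresses more. Under the design assumptions that is Control, so the table would understate Control recurrence more than Test recurrence and narrow the apparent difference. The endpoint is a named secondary effectiveness endpoint, reported by arm at each visit.

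**Working it through.** **Planning rates.** The documents give no figure for the rhythm endpoint, so the check uses the sample-size assumptions in SAP 6: 3-year progression of 5% in Test and 15% in Control, the latter being 25% diluted by 50% cross-over. With constant hazards, −ln[ln(0.95)/ln(0.85)] = 1.1532 (stated: 1.1541). A pooled two-proportion calculation for 15% v 5%, one-sided 0.025, 85% power, gives 161 per arm, as stated. The rates are read correctly.

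**Share progressed by year t.** Control: 1 − 0.85^(t/3). Test: 1 − 0.95^(t/3). Drop-out is ignored.

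| Time | Control | Test | Control − Test |
|---|---|---|---|
| Year 1 | 5.27% | 1.70% | 3.6 points |
| Month 18 | 7.80% | 2.53% | 5.3 points |
| Year 2 | 10.27% | 3.36% | 6.9 points |
| Month 30 | 12.67% | 4.18% | 8.5 points |

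**Who is affected.** Let s be the start of the window and t the visit. A subject who progresses between s and t normally has AF/AT documented in that window and is counted. Only those progressed by s are at risk. If phone contacts count as visits:

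- Year 2 (window opens at Month 18): 7.8% v 2.5%, or 12.6 v 4.1 of 161 per arm.
- Month 30 (window opens at Year 2): 10.3% v 3.4%, or 16.5 v 5.4 of 161 per arm.

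**Effect on the difference.** Let r be recurrence among unprogressed subjects. The documents give no value, so r is an assumption.

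- All progressed subjects counted as AF/AT: p(t) + [1 − p(t)]·r
- As the SAP reads, with no later recording: the same minus p(s)

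The shift is p(s) in Control minus p(s) in Test, whatever r is: 7.80 − 2.53 = 5.3 points at Year 2 and 10.27 − 3.36 = 6.9 at Month 30.

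Year 2, r = 30% v 15%:
- Counted: Control 10.27 + 89.73 × 0.30 = 37.19%; Test 3.36 + 96.64 × 0.15 = 17.86%; difference 19.3.
- As written: 37.19 − 7.80 = 29.38%; 17.86 − 2.53 = 15.33%; difference 14.1.

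Month 30, r = 30% v 15%:
- Counted: 12.67 + 87.33 × 0.30 = 38.87%; 4.18 + 95.82 × 0.15 = 18.56%; difference 20.3.
- As written: 38.87 − 10.27 = 28.60%; 18.56 − 3.36 = 15.20%; difference 13.4.

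Year 2, r = 20% v 10%:
- Counted: 10.27 + 17.95 = 28.21%; 3.36 + 9.66 = 13.03%; difference 15.2.
- As written: 15.2 − 5.3 = 9.9.

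**Clinic visits only.** The Year 2 window then opens at Year 1. The shift is 5.27 − 1.70 = 3.6 points, so 19.3 becomes 15.8, and there is no Month 30 row.

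**Treated as missing instead.** At Year 2 with r = 30% v 15%: 29.383/92.195 = 31.871% and 15.325/97.468 = 15.723%, a difference of 16.1 points. Month 30 gives the same 16.1, because the conditional half-year risk is constant. Against 19.3 and 20.3 the difference is still understated, by less.

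**The case against.** The strongest reply is that no sentence in the SAP labels progressed subjects as non-recurrent. The 8.1 denominator is a general default, and SAP 13.2 says sizes shown with summary statistics are subjects with non-missing values. A programmer might drop progressed subjects, in which case the difference would not keep shrinking with time. This stands as a limit on certainty, but it does not rescue the plan. Section 10.6.3 makes no exception to the default, and dropping subjects because they progressed is itself informative.

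Four stronger readings are tempting and are not supported.

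- A reader might infer that everyone progressed by Year 2 (10.3% v 3.4%) is lost at Year 2. The window rule says otherwise: those who progress within the window are counted.
- A reader might infer that progressed subjects have no further tracing at all. The protocol says monitoring is not required and interim visits are not needed. Unscheduled ECGs are still collected (11.2.1), unscheduled cardiovascular visits have their own form (11.2.2), and subjects return at Year 3, where a standard-of-care ECG may show AF.
- A reader might infer that all progressed subjects remain in AF/AT. The endpoint is also met by cardioversion after 48 hours, and SAP 7 foresees Control ablation after the endpoint, so some may be in sinus rhythm.
- A reader might infer a bias that favours ablation. Under the planning rates it runs the other way.

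It is also fair to say that Protocol 13.16 lists the endpoint as descriptive and that progression is reported separately by Kaplan-Meier.

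**Conclusion.** The point holds. Following SAP 10.6.3 with the 8.1 default normally shows subjects who progressed before the window opened as free of recurrent AF/AT at later interim visits. The Control-minus-Test difference is understated by up to 5.3 points at Year 2 and 6.9 at Month 30, or 3.6 at Year 2 if only clinic visits count.

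These shifts rest on the planning rates, constant hazards and no drop-out. They are upper bounds because they assume that every progressed subject stays in AF/AT and has no later recording. The recurrence levels in the worked differences are assumptions, but the size of the shift does not depend on them. The sinus-rhythm percentage has the same gap, since its details are left to programming.

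The primary analysis is unaffected, and nothing here implies a false claim of benefit. The change is worth making because a named secondary endpoint would otherwise contradict the progression analysis.

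**What to change.** In SAP 10.6.3:

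1. From the adjudicated progression date onward (already derived under SAP 8.3), report subjects with no rhythm recording in the window as a separate category, for example 'progressed to persistent AF/AT, not monitored', by arm and visit. Do not place them under no recurrent AF/AT.
2. State the per-visit denominator for both rhythm percentages, and say whether phone contacts count as visits.
3. Show recurrent AF/AT alone and combined with the progressed category.

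No new data are needed. The cost is one derivation rule and one more row per table. The combined figure may include some subjects restored to sinus rhythm, which is why the separate row should be shown beside it.

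### Up to about month 18 (year 2 if only clinic visits count), the by-visit recurrent AF/AT percentage in SAP 10.6.3 is confounded with monitoring intensity and cannot be read as a disease trend.

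*SAP*

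**What the plan says.** SAP 10.6.3 defines the recurrence variable by a window and a rule. On the window: "This variable will also refer to the time period after previous visit up to the visit analyzed". The rule is any-positive: "A subject has recurrent AF/AT if AF or AT is documented at any TTM, Holter or ECG within this timeframe". The result is summarised by treatment group at each follow-up visit. The section does not say whether the phone contacts at months 9, 18 and 30 count as visits, and it makes no allowance for the number of recordings or the length of the window. The companion variable, percentage in sinus rhythm, uses only data captured at the visit.

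Protocol 11.2.1 sets the TTM schedule for both arms ("TTM monitoring (both groups) will be conducted as follows"):

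- "Start TTM monitoring at Day 104", which is the last day of the month 3 visit window (Days 76 to 104).
- "Weekly TTM monitoring as from Day 104 until Day 300".
- Monthly from Day 300 to the 3-year visit.
- Daily when symptoms are present, outside this grid.

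In Protocol Table 1, ECGs are collected only when done as standard of care, and Holter does not appear. Arrhythmia monitoring stops once a subject has progressed to persistent AF/AT (Protocol 11.2.1). The default denominator for percentages is the whole study population (SAP 8.1). Protocol 13.12.3 plans the percentage over the 3-year follow-up; the visit-by-visit windows come from the SAP.

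**The concern.** Under an any-positive rule, the chance of being called recurrent rises with the number of recordings in the window. That number changes sharply during the first half of follow-up for reasons unrelated to disease. A table of percentages by visit invites the reader to follow them as a time course. In a trial about progression, an early rise and later fall could be taken for worsening and then recovery, and real worsening could be hidden. The size of the gap between arms would also change with the schedule even if the underlying contrast were constant.

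**Working it through.** The documents state no expected percentage for this endpoint, so there is no plan figure to reproduce.

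**Step 1. Count scheduled TTM per interval.** Inputs: weekly recordings on Days 104, 111, …, 300, which is (300 − 104)/7 + 1 = 29; then every 30 days on Days 330, 360, …, 1080, which is (1080 − 330)/30 + 1 = 26. Target visit days are 90, 180, 270, 365, 545, 730, 910 and 1095 (my reading of the visit names in Table 1).

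| Visits counted | M3 | M6 | M9 | Y1 | M18 | Y2 | M30 | Y3 |
|---|---|---|---|---|---|---|---|---|
| All | 0 | 11 | 13 | 7 | 6 | 6 | 6 | 6 |
| Clinic only | 0 | 11 | – | 20 | – | 12 | – | 12 |

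With every visit at the early or every visit at the late edge of its window, M6 ranges from 9 to 15 and Y1 from 4 to 10 (all visits). The later counts stay between 5 and 7.

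**Step 2. Hold disease constant.** Let p be the chance that one scheduled recording shows AF/AT. The documents do not give p; I assume 1% to 10%, independent between recordings. Then the percentage recurrent = 1 − (1 − p)^n.

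At p = 5%, all visits: n = 11 gives 1 − 0.95^11 = 43%; n = 13 gives 49%; n = 7 gives 30%; n = 6 gives 26.5%. Clinic visits only: n = 20 gives 64% at Y1 and n = 12 gives 46% at Y2 and Y3.

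| p | M9 to M18 (all visits) | Y1 to Y2 (clinic only) |
|---|---|---|
| 1% | 12% to 6% | 18% to 11% |
| 2% | 23% to 11% | 33% to 21.5% |
| 5% | 49% to 26.5% | 64% to 46% |
| 10% | 75% to 47% | 88% to 72% |

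**Step 3. Can real worsening be hidden?** If p doubles from 5% at M9 to 10% at M18, the table reads 49% (n = 13) and then 47% (n = 6).

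**Step 4. Gap between arms.** Assume constant p of 2% in Test and 8% in Control. The gap is 0.98^n − 0.92^n. All visits: 0, 40, 43, 31, then 28 points. Clinic visits only: 0, 40, 48, 42, 42 points. The sign never changes; the size moves with n.

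**Step 5. Relax independence** (beta-binomial, p = 5%, M9 to M18). Correlation 0.1: 35% to 22%. Correlation 0.3: 22% to 16%. Correlation 0.5: 15% to 12%.

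**Step 6. Add symptom-triggered positives** at an assumed rate r per year: 1 − (1 − p)^n × exp(−r × days/365). With r = 0.25 and p = 5%, M9 to M18 goes from 52% to 35%. With r = 1 and p = 5%, it goes from 60% to 55%. With r = 1 and p = 2%, it goes from 40% to 46%, so the direction reverses.

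**Step 7. Equalise effort.** One recording per 30 days gives six per 180-day window, so 1 − 0.95^6 = 26.5% in every full window under constant p = 5%.

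**The case against.** The strongest reply is that the randomised comparison is safe. Both arms share one TTM schedule, the endpoint is descriptive, and there is no trend test or success criterion. This stands: at any one visit, the schedule does not bias the direction of the difference between arms.

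Three further points also stand. First, the scheduled count is flat from M18 (Y2 on clinic visits). A reader might infer that the whole 3-year trend reflects the schedule and not the disease; the documents do not support that for the second half of follow-up. Second, symptom-triggered TTM, ECGs and Holter also count. They partly reflect disease and accumulate with interval length, so neither the size nor the direction of the artefact is fixed. For the same reason the 0% at M3 applies to scheduled TTM only, because an ECG or Holter can make a subject positive there. Third, a reader might expect a late narrowing of the arm gap that mimics a waning ablation effect. That depends on counting phone contacts as visits; on clinic visits the late gap in Step 4 (42 points) is no smaller than at M6 (40).

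None of this restores comparability over the first half of follow-up. An artefact of unknown size and direction still cannot be separated from disease without the recording counts.

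**Conclusion.** The point holds in a limited form. Up to about M18, or Y2 on clinic visits, both the by-visit percentage and the size of the arm gap are confounded with monitoring intensity. This follows from the counts alone, on either reading of what a visit is. How far the figures move rests on assumptions outside the documents: under independence and constant p, the fall from M9 to M18 is roughly by half for p of 1% to 5% and by a little over a third at 10%. Correlation reduces it, and symptom-triggered recordings can reduce or reverse it. Because this is a listed secondary endpoint without a formal test, the matter is worth correcting but does not threaten the trial's main conclusion.

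**What to change.** In SAP 10.6.3:

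- Add a by-subject recurrence table from scheduled TTM at one common cadence from Day 104: the first scheduled recording in each 30-day window, reported in equal-length windows (for example 180 days).
- Give no TTM-based figure for the M3 interval.
- Use as denominator the subjects with scheduled recordings in the window. Show those already progressed to persistent AF/AT as a separate category. Their monitoring has stopped, and under the default whole-population denominator they could otherwise pass as free of recurrence.
- Keep the any TTM, Holter or ECG table. Add the number of recordings per subject by interval and arm, state whether phone contacts count as visits, and note that the percentages are not comparable across visits up to about M18/Y2.

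The cost is SAP wording and one derivation rule on data the protocol already collects, provided the TTM data distinguish scheduled from symptom-triggered transmissions. Thinning discards some weekly recordings in the common-cadence table, but they remain in the other one.

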#### Effectiveness:

- Rate and time to persistent AF/AT at 1 year and 2 years, rate of persistent AF/AT by number of ablations at 3 years.
- Number of repeat ablations and new AAD drugs per subject throughout 3 years follow-up.
- Rhythm (% subjects in SR, % subjects with recurrent AF) throughout 3 years follow-up.
- Subject's pre-existing or new onset/worsened condition(s), that may be associated with AF progression, will be collected at baseline and at each follow up visit throughout the 3-year study period; parameters include subject's age and gender and the following assessments of non-AF health status: LA size; HATCH Score; blood pressure; NYHA Functional Classification of heart disease; diabetes; lipid profile; renal function and, dementia.d

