#### **13.12.3 Rhythm Throughout 3 Years Follow-up**

To analyze this secondary effectiveness endpoint, rhythm (% subjects in sinus rhythm, % subjects with recurrent AF) throughout 3 years follow-up, the number of subjects and percentage of subjects with sinus rhythm and the number of subjects and percentage of subjects with recurrent AF/AT during the 3 year follow-up time will be summarized and listed by the two groups. The analyses will be performed in both ITT and PP populations.

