#### 13.14.2 Quality of Life

Quality of Life (QoL) status will be compared to baseline at 3 months, 6 months, 1 year, 2 years and 3 years. QoL will be measured by the EQ-5D and AFEQT questionnaires. Descriptive statistics for the baseline and changes-from-baseline measurements of the summary scores of these two measurement scales at follow-up visits will be summarized and listed by treatment groups. The analyses will be performed in the PP population. Paired-sample test will be used to test whether the change-from-baseline values differs from zero (e.g., paired t-test) within each treatment group. A two-sample comparison of the two groups with respect to changes-from-baseline in QoL will be performed using general linear models, including the baseline value as a covariate and assessing treatment group differences.

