5. CHANGES TO PLANNED ANALYSIS

5.1 Changes for the final analysis

As the study was terminated early, without having met primary effectiveness or futility criteria at the most recent interim analysis, it is not fully obvious which alpha level to use for the primary efficacy analysis. However as the number and time points of the interim analyses had not been fixed in advance, it was decided to spend all alpha remaining for the final analysis, in other words to spend what is left from the total alpha. Moreover, after further discussion, it has been decided to update the calculation of the primary endpoint to use procedure date as start date for time to event calculation rather than randomization date (see section 8.3).

It also was decided to delete some of the analyses originally planned in the protocol:

- For secondary endpoint “factors associated with AF disease progression”, only the main analyses will be performed, and some of the supporting models were deleted
- Analysis of site heterogeneity will not be performed

Moreover, a sensitivity analysis for the primary endpoint and first secondary endpoint was added, using an alternative definition for the primary endpoint based on the consensus statement of the HRS (Heart Rhythm Society, 2017).

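### SAP 10.6.3 plans recurrent AF/AT only visit by visit, so the share of subjects with any recurrence over 3 years, the natural reading of protocol 13.12.3, is not a planned output

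*SAP*

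**What the plan says.** Protocol 10.2 lists the secondary endpoint as "Rhythm (% subjects in SR, % subjects with recurrent AF) throughout 3 years follow-up". Protocol 13.12.3 gives its analysis: "percentage of subjects with recurrent AF/AT during the 3 year follow-up time will be summarized and listed by the two groups". Neither section names a visit or an interval. Protocol 13.16 gives the method as descriptive statistics, in the ITT and PP populations.

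SAP 10.6.3 gives recurrent AF/AT an operational definition that looks back over one interval only: "This variable will also refer to the time period after previous visit up to the visit analyzed (including data captured at the visit analyzed"). Any TTM, Holter or ECG showing AF or AT in that window is enough to qualify. The planned summary is also by visit: "the number and percentage of subjects with recurrent AF/AT at each visit during the 3 year follow-up time will be summarized".

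The only rhythm table in SAP 15.1 is 14.2.9, Heart Rhythm. SAP 10.6.1 covers persistent AF/AT only. No section, table or figure plans any recurrence over three years or time to first recurrence.

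SAP 5.1 records departures from the protocol, including deletions ("It also was decided to delete some of the analyses originally planned in the protocol"), but does not mention the rhythm endpoint. Nor does SAP 5.2.

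On follow-up after progression, protocol 11.2.1 says: "Subjects who reach the primary endpoint (progress to persistent AF/AT) will only have to return for the final visit at 3 years". TTM is discontinued at the same point. SAP 8.1 sets the default percentage denominator as everyone in the study population for that treatment group.

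**The concern.** A three-year proportion and a series of interval proportions answer different questions. The first says how many subjects in each arm had AF/AT again. The second says how many had it in each window, without showing whether they were the same subjects. If the SAP is followed as written, the report will contain only the second. Two arms with identical by-visit percentages could then differ widely in the number of subjects affected, and the planned table would not show it.

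A further problem sits inside the by-visit table. Subjects who progress to persistent AF/AT have clearly recurred, yet scheduled monitoring stops for them. SAP 10.6.3 gives no rule for counting them at later visits. With the whole group as denominator and no recording in the window, they can fall among the non-recurrent.

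**Working it through.** The documents give no sample size, power or alpha for this endpoint, so there is no plan figure to reproduce. The check is a comparison of texts, followed by two illustrations.

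**1. Texts side by side**

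| | Protocol 13.12.3 | SAP 10.6.3 |
|---|---|---|
| Window for recurrence | The 3-year follow-up | Since the preceding visit |
| Output | Count and percentage by group | Count and percentage by group at each visit |
| Visits named | None | Each follow-up visit |

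Where the protocol wants analysis by visit, it names the visits, as in 13.14.2: "Quality of Life (QoL) status will be compared to baseline at 3 months, 6 months, 1 year, 2 years and 3 years". It does not do so for rhythm.

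**2. Can the by-visit percentages give the 3-year share?**

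Let p be the share recurring in each of K intervals (taken as equal for simplicity).

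- Lower bound, same subjects every time: p.
- Upper bound, different subjects every time: min(1, K × p).
- Independent intervals: 1 − (1 − p)^K.

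The SAP does not say whether phone contacts count as visits. Protocol 11.2.1 lists five clinic visits (3 and 6 months; 1, 2 and 3 years) and three phone contacts (9, 18 and 30 months), so K is 5 or 8. The documents give no interval recurrence rate; the values of p below are assumptions.

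| Assumed p | K = 5: range (independent) | K = 8: range (independent) |
|---|---|---|
| 5% | 5–25% (23%) | 5–40% (34%) |
| 10% | 10–50% (41%) | 10–80% (57%) |
| 20% | 20–100% (67%) | 20–100% (83%) |

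For p = 10%: 1 − 0.9^5 = 0.41 and 1 − 0.9^8 = 0.57. With five visits at 10% in both arms, one arm could have 10% of its subjects affected and the other 50%.

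**3. How many progressed subjects could be miscounted?**

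The sample-size formula (protocol 13.4, SAP section 6) uses constant hazards, with 85% of control and 95% of test subjects free of progression at 3 years. Progression by year t is then 1 − 0.85^(t/3) and 1 − 0.95^(t/3).

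- Five clinic visits: subjects who progressed before year 1 have no scheduled monitoring in the interval ending at year 2. That is 1 − 0.85^(1/3) = 5.3% of control and 1 − 0.95^(1/3) = 1.7% of test, a gap of 3.6 points.
- Eight contacts: subjects who progressed before year 2 have none in the interval ending at month 30. That is 1 − 0.85^(2/3) = 10.3% and 1 − 0.95^(2/3) = 3.4%, a gap of 6.9 points.

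These are ceilings under the design assumptions, because an unscheduled ECG could still document AF in such a subject. The final 3-year visit is kept for everyone.

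**The case against.** The strongest reply is that the SAP clarifies the endpoint and does not change it. The protocol never uses the word cumulative and gives no rule that a subject counts once. The endpoint pairs recurrence with the percentage in sinus rhythm, which is naturally a point-in-time measure, and throughout 3 years can loosely mean repeated over follow-up. That ambiguity is real, so a reader should not state as fact that the protocol defines a cumulative count. Even so, the wording of 13.12.3 and the contrast with quality of life make the 3-year proportion the more natural reading. If by-visit was intended, SAP section 5 is the place to say so.

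Other stronger readings also go too far:

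- **Eight intervals.** A reader might infer eight percentages from the assessment schedule. The SAP says only each follow-up visit; five is equally consistent.
- **Uneven monitoring.** No scheduled TTM before Day 104, weekly to Day 300 and monthly after that makes the by-visit figures hard to compare over time. The same schedule applies in both arms and limits a 3-year figure too, so it is no argument for one summary over the other.
- **Kaplan-Meier as the protocol's estimate.** Protocol 13.16 specifies descriptive statistics. Time to first recurrence would be an addition.
- **The information is lost.** It is not: listing 16.2.17.3 includes heart rhythm by subject, so the figure could be derived. However, SAP 4.2 treats analyses not identified in the SAP as post hoc, an awkward label for a prespecified secondary endpoint.

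Finally, no test or alpha depends on this endpoint. That stands, and it limits the weight of the point.

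**Conclusion.** The point holds in a limited form. On the natural reading of protocol 13.12.3, the share of subjects in each arm with any recurrent AF/AT over three years is a secondary result. The SAP replaces it with interval percentages, does not declare the change, and plans no output that gives it. At an assumed 10% per interval, the by-visit figures leave the 3-year share anywhere between 10% and 50% (five visits) or 10% and 80% (eight contacts). The rates and the number of intervals are assumptions, but the conclusion that one quantity does not determine the other does not depend on them.

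The counting of progressed subjects is a second, smaller gap. It rests on the default denominator in SAP 8.1 applying, since SAP 10.6.3 gives no other. The impact is modest: the endpoint is descriptive, the primary analysis is untouched, and the data exist.

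**What to change.** In SAP 10.6.3 and table 14.2.9:

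1. Add, by randomized group, how many subjects and what percentage had any documented AF/AT recurrence through 3 years. Count progression to persistent AF/AT as recurrence, and use the SAP 8.3 start dates (procedure for test, randomization for control).
2. Support it with a Kaplan-Meier estimate of time to first recurrence, because follow-up varies after the early termination noted in SAP 5.1.
3. Keep the by-visit summary, and state how subjects who have already progressed are counted in it.
4. List the by-visit definition in SAP section 5 as a departure from, or clarification of, protocol 13.12.3.

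The cost is one extra row or table from rhythm data already collected and listed, plus a few sentences of text. The TTM schedule will still limit any recurrence figure, and a footnote should say so.
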